10.4 VITAL SIGNS

Vital signs will consist of blood pressure (systolic and diastolic blood pressure, mmHg), pulse rate (beats per minute), and respiratory rate (breaths/min), and body temperature collected while sitting, following a rest period of at least 3 minutes. Vital sign values and change from baseline in the vital signs will be summarized for each treatment group.

10.5 PHYSICAL EXAMINATION

Number and percent of subjects with abnormal physical examination findings at Screening and Week 25 will be summarized by body system for each treatment group and overall. Physical examination data for each subject will also be presented in a listing.

10.6 12-LEAD ELECTROCARDIOGRAM (ECG)

12-Lead ECGs will be performed at screening, Day 1, Day 8, and all subsequent scheduled visits through Week 25 after the subject has been resting in a recumbent/supine position for at least 3 minutes. The ECG variables will include ventricular heart rate and the PR, QRS, QT, QTcB and QTcF intervals. The ECGs will be signed and dated by a medically-qualified individual to confirm review of the ECG and verify whether any abnormalities are clinically significant.

Number and percent of subjects in each ECG finding category (normal, abnormal not clinically significant, and abnormal and clinically significant), will be summarized for each visit by each treatment group and overall. Summary statistics will be presented for the actual value and change for each ECG parameter.

The number and percent of subjects with QT, QTcB and QTcF intervals < 450 msec, 450 to <480, 480 to <500 and greater than/equal to 500 msec at each visit and overall (at any visit) will be summarized. Additionally, the number and percentage of subjects with changes in these parameters of <30 msec, 30

to <60 msec and greater than/equal to 60 msec will be summarized at each visit and overall (at any visit).

10.7 INJECTION SITE EXAMINATION

Injection site reactions can occur with injection of CAM2038 or placebo. The injection site will be visually inspected for evidence of erythema, edema, itching, pain, infection, bleeding, abnormal healing and any other abnormalities. Summaries of all injection site reactions as well as of clinically significant injection site reactions will be presented.

All AEs, AEs that are associated with injection procedures, and other AEs (not associated with injections) will be summarized.

11.0 IDENTIFICATION AND SUMMARY OF PROTOCOL DEVIATIONS

Major protocol deviations from entry criteria and treatment compliance will be summarized as far as they can be extracted from numeric or coded study data.

12.0 DATA QUALITY ASSURANCE

Accurate and reliable data collection will be ensured by verification and cross check of the CRFs against the investigator's records by the study monitor (source document verification) and by the maintenance of a drug-dispensing log by the investigator. Collected data will be entered into a computer database and subject to electronic and manual quality assurance procedures.

14.0 APPENDICES

14.1 APPENDIX A - IMPUTATION ALGORITHM FOR PARTIAL AND MISSING DATES

This section describes missing date imputation methods.

For Adverse Events

If onset date is completely missing, onset date is set to date of randomization.

If (year is present and month and day are missing) or (year and day are present and month is missing):

- If year = year of randomization, then set month and day to month and day of randomization
- If year < year of randomization, then set month and day to December 31.
- If year > year of randomization, then set month and day to January 1.

If month and year are present and day is missing:

- If year=year of randomization and
 - If month = month of randomization then set day to day of first dose
 - If month < month of first dose then set day to last day of month
 - If month > month of first dose then set day to first day of month
- If year < year of randomization then set day to last day of month
- If year > year of randomization then set day to first day of month

For all other cases, set onset date to date of randomization.

Concomitant Medications/Medical History

For start date

- If start date is completely missing, start date will not be imputed.
- If (year is present and month and day are missing) or (year and day are present and month is missing), set month and day to January 1.
- If year and month are present and day is missing, set day to 1st day of month.

For end date

- If end date is completely missing, end date will not be imputed.
- If (year is present and month and day are missing) or (year and day are present and month is missing), set month and day to December 31.
- If year and month are present and day is missing, set day to last day of the month.

Note: that if both start and end dates are missing then the medication will be classified as concomitant.

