10.4.1.1. Adverse Event Reporting

All AEs must be entered on the AE CRF, regardless of causality or severity. AEs include new AEs, worsening baseline conditions, clinically significant laboratory findings, disease-related signs and symptoms that were not present at baseline, and any events or findings that the Investigator considers clinically significant.

Disease-related signs and symptoms that are present at baseline should not be recorded as AEs unless they worsen in severity or increase in frequency.

Information collected concerning AEs will include the following:

- Name of the event
- Onset date
- Resolution date
- Severity (i.e., mild, moderate, or severe)
- Relationship to trial drug
- Action and outcome
- Seriousness of event

All AEs will be documented and followed from the time the subject has signed the ICF until 14 days after the Follow-up Visit at Week 29 or early termination. SAEs and AEs that have been designated as related to trial drug will be followed until resolution or stabilization.

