10.2 ADVERSE EVENTS

Each AE and serious adverse event (SAE) term recorded on the CRFs will be mapped to a primary system organ class (SOC) and a preferred term using the MedDRA dictionary. The investigator will assess AE severity and relationship to the study treatment.

Columbia Suicide Severity Rating Scale (C-SSRS) will be summarized.

A treatment-emergent adverse event (TEAE) is defined as any AE with an onset date on or after date of randomization, or any ongoing event on the date of first dose that worsens in severity after date of randomization. Only TEAEs with an onset date prior to date of last dose + 30 days will be tabulated in

summary tables. For the purpose calculating treatment emergence and inclusion in summary tables, incomplete onset dates will be imputed as detailed in Appendix A.

TEAEs will be summarized by the number and percent of subjects in each primary SOC and preferred term. Patients will be counted only once for each primary SOC and each preferred term. Summary tables of TEAEs by primary SOC, preferred term and intensity will be provided. If a subject has more than one AE coded to the same preferred term, the subject will be counted only once for that preferred term by using the event with the highest intensity. Similarly, if a subject has more than one AE within a primary SOC category, the subject will be counted only once in that SOC category by using the event with the highest intensity. AEs by primary SOC, preferred term and relationship to study drug will be provided as well. If a subject has more than one AE coded to the same preferred term, the subject will be counted only once for that preferred term by using the most related event. Similarly, if a subject has more than one AE within a primary SOC category, the subject will be counted only once in that primary SOC category by using the most related event. In addition, SAEs by primary SOC and preferred term will be provided. Deaths and SAEs will be summarized similarly to AEs. All TEAE tables will also include the total number of events, counting multiple events per patient.

Injection related AEs, other (non-injection related) AEs as well as all AEs will be presented by treatment group and overall. Summaries of these AE subsets will be presented for the following categories:

- Study drug related
- Intensity
- Relationship to injection
- Possibly study drug related by intensity
- Reasonably injection related by intensity
- Serious

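### SAP Appendix A can give some partly dated screening adverse events an onset after their own resolution and count them as treatment-emergent, because no AE rule checks the resolution date

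*SAP*

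**What the plan says.** SAP 10.2 makes the onset date decisive: "A treatment-emergent adverse event (TEAE) is defined as any AE with an onset date on or after date of randomization". The only other route into the definition is an event still ongoing at first dose that later worsens. For deciding emergence and inclusion in the summary tables, "incomplete onset dates will be imputed as detailed in Appendix A".

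For AEs, SAP 14.1 (Appendix A) moves an incomplete onset to Day 1 in these cases:

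- Day missing, month and year matching randomization: "If month = month of randomization then set day to day of first dose".
- Month missing, with or without the day: "If year = year of randomization, then set month and day to month and day of randomization".
- Nothing recorded: "If onset date is completely missing, onset date is set to date of randomization".
- Any remaining pattern: "For all other cases, set onset date to date of randomization".

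It keeps the event before treatment when the known part of the date is clearly earlier. For a missing day in an earlier month of the same year, "If month < month of first dose then set day to last day of month". Partial onsets in an earlier year go to the end of that year, or to the end of the recorded month.

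In Protocol 10.4.1.1, "All AEs will be documented and followed from the time the subject has signed the ICF", and the resolution date is among the items recorded for each event. Protocol 7.1.1 allows screening up to 3 weeks before Day 1.

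**The concern.** Screening events will be in the AE data, some of them already over when the subject is randomized. For those, the resolution date settles the question: the event was not treatment-emergent, whatever its exact onset. Appendix A does not consult that date, so in the branches above it replaces a known answer with a wrong one and can create a record whose onset is later than its end.

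Such an event would be counted in the overall TEAE tables, in any subset table for which it qualifies, and in the summary of TEAEs during the first week after randomization (SAP 10.2). That summary describes the week in which both arms start buprenorphine, so a few misplaced events would show there first.

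The SAP handles medications differently. SAP 8.0 assigns a medication that clearly stopped before the first study treatment to the prior table, which is a stop-date check. AEs have no counterpart.

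**Working it through.** The plan gives no figure to reproduce. The check applies the rules to example records and then works out how often the same-month branch is reached.

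**Inputs**

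- TEAE if onset is on or after randomization (SAP 10.2).
- Imputation branches (SAP 14.1).
- First dose and randomization both on Day 1 (Protocol 7.1.2 and Table 3), so the appendix's mix of *first dose* and *randomization* makes no difference here.
- Screening window of at most 21 days (Protocol 7.1.1).
- Assumptions: onsets spread evenly over the days before randomization, and randomization dates spread evenly over a 366-day year.

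**Single records.** Consent 3 March 2016, event resolved 9 March, randomization 20 March:

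| Recorded onset | Imputed onset | Class |
|---|---|---|
| March 2016, no day | 20 March 2016 | TEAE |
| 2016 only | 20 March 2016 | TEAE |
| Nothing | 20 March 2016 | TEAE |

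In all three the onset falls 20 − 9 = 11 days after the event ended. For contrast, a partial onset of February 2016 is imputed to 29 February, and 2015 alone to 31 December 2015. Neither is a TEAE.

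**Share of day-missing records caught, all screening onsets.** An onset *j* days before randomization is in the same calendar month unless randomization falls in the first *j* days of a month. For *j* up to 21 that leaves 366 − 12*j* of the 366 randomization dates. Averaging over *j* = 1 to *W*, where the mean lag is (*W* + 1)/2:

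share = 1 − 12 × (*W* + 1)/2 ÷ 366 = 1 − 6(*W* + 1)/366

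- *W* = 7: 1 − 48/366 = 86.9%
- *W* = 14: 1 − 90/366 = 75.4%
- *W* = 21: 1 − 132/366 = 63.9%

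A full enumeration of dates gives the same values (for 21 days, 4,914 of 7,686 pairs).

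**Share among events that ended before randomization.** This is the group at issue. If the event lasts *D* days (resolution = onset + *D*) and must end before Day 1, the lag runs from *D* + 1 to 21, with mean (*D* + 22)/2:

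share = 1 − 6(*D* + 22)/366

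- *D* = 3: 1 − 150/366 = 59.0%
- *D* = 7: 1 − 174/366 = 52.5%
- *D* = 14: 1 − 216/366 = 41.0%

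**Other branches.** With month and day missing, the year matches unless the window crosses 1 January. The share is 1 − (mean lag)/366. For all onsets in a 21-day window that is 1 − 11/366 = 97.0%. For events already ended it is 1 − 12.5/366 = 96.6% (*D* = 3) to 1 − 18/366 = 95.1% (*D* = 14). With the onset wholly missing it is 100%, which only restates the rule.

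**After a resolution-date check.** The share is 0% for events known to have ended before randomization, and unchanged for all others.

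**The case against.** The strongest reply is that moving an uncertain onset toward treatment is a deliberate, conservative convention: it overcounts TEAEs rather than hiding them. That stands where timing really is unknown. It does not cover a record whose own end date shows the event was over.

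The second reply is that the affected set is tiny. A record needs an incomplete onset, a resolution known to precede randomization, and a start inside a window of at most 3 weeks. Medical history is collected separately (Protocol 10.1.3), onset date is a listed AE item, and entries are checked against source (Protocol 11.1). The AE data are also listed (SAP Listing 16.2.7.1), so the true end date stays visible. All of this stands, and it is why the point is minor.

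A reader might infer more than the documents support:

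- *Every partly dated screening event becomes a TEAE.* No: the earlier-month and earlier-year branches keep such events before treatment.
- *The event enters every TEAE table.* No: the injection-site, serious, drug-related and discontinuation tables in Appendix B take only events that meet those criteria.
- *Day 1 is reported separately.* No: SAP 10.2 plans a first-week summary.
- *The 64% applies to events that ended before randomization.* No: it covers all screening onsets. Events that must also have ended start earlier, and the share is lower.
- *The arms are biased against each other.* Nothing shows this. The events precede randomization, one rule serves both arms, and SAP 10.0 pre-specifies no formal safety comparison.

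**Conclusion.** The point holds as a minor one. In the branches identified, Appendix A can assign an onset later than the recorded resolution and class a known pre-treatment event as treatment-emergent.

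For a day-missing record the same-month branch is reached in about 87%, 75% and 64% of cases for screening windows of 7, 14 and 21 days. Among events that ended before Day 1 in a 21-day window the figure is about 59% to 41% for durations of 3 to 14 days. These shares are conditional on an incomplete date and rest on evenly spread onsets and randomization dates.

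The documents do not say how many records will have incomplete onsets, so the effect on any TEAE rate cannot be sized. It is probably small and is expected to balance between arms. The primary and other efficacy analyses are untouched.

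**What to change.** Add to the AE part of Appendix A:

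*If the resolution date is known to be before the date of randomization, the event is not treatment-emergent and the imputed onset may not be later than the resolution date; otherwise the rules above apply.*

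A partial resolution date is enough when its known part already places the end before randomization. Events that are ongoing, or whose end date is missing, keep the present conservative imputation. The change also brings AEs into line with the stop-date logic that SAP 8.0 uses for medications.

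The cost is one sentence in the SAP and about one line of code, with no new data. SAP 3.0 allows the plan to be revised until it is finalized before database lock and unblinding, so the change can be made then without prejudice.

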14.2 APPENDIX B – LIST OF TABLES, LISTINGS, AND FIGURES

List of Tables

Number	Title
TABLE 14.1.1.1	Summary of Disposition of Patients (ITT Population)
TABLE 14.1.1.2	Summary of Disposition of Patients (Safety Population)
TABLE 14.1.1.3	Summary of Disposition of Patients (mITT Population)
TABLE 14.1.1.4	Summary of Disposition of Patients (Per Protocol Population)
TABLE 14.1.2.1	Summary of Demographics and Baseline Characteristics (Safety Population)
TABLE 14.1.2.2	Summary of Demographics and Baseline Characteristics (ITT Population)
TABLE 14.1.2.3	Summary of Demographics and Baseline Characteristics (Per Protocol Population)
TABLE 14.1.4	Summary of Psychiatric History (Safety Population)
TABLE 14.1.5.1	Summary of Prior Medications (Safety Population)
TABLE 14.1.5.2	Summary of Concomitant Medications (Safety Population)
TABLE 14.1.6	Summary of Substance Abuse Treatment History (Safety Population)
TABLE 14.2.1.1	Analysis Results for Primary Efficacy Variable Responder Rate (ITT Population)
TABLE 14.2.1.2	Analysis Results for Primary Efficacy Variable Responder Rate (Per Protocol Population)
TABLE 14.2.2.1	Analysis Results for CDF of Percentage of Urine Samples Negative for Illicit Opioids Supported by Self-reported Illicit Opioid Use Results Over Weeks 5-25 (ITT Population)
TABLE 14.2.2.2	Analysis Results for CDF of Percentage of Urine Samples Negative for Illicit Opioids Supported by Self-reported Illicit Opioid Use Results Over Weeks 5-25 (Per Protocol Population)
TABLE 14.2.3.1	Analysis Results for Time to Sustained Abstinence of Opioid Use (ITT Population)
TABLE 14.2.3.2	Analysis Results for Time to Sustained Abstinence of Opioid Use (Per Protocol Population)
TABLE 14.2.4.1	Analysis Results for Percent of Subjects Remaining in the Study (Retention Rate) (ITT Population)
TABLE 14.2.4.2	Analysis Results for Percent of Subjects Remaining in the Study (Retention Rate) (Per Protocol Population)
TABLE 14.2.5.1	Analysis Results for Response Rate in Phase 1 Based on Primary Responder Definition (ITT Population)
TABLE 14.2.5.2	Analysis Results for Response Rate in Phase 2 Based on Primary Responder Definition (ITT Population)
TABLE 14.2.6.1	Analysis of Percentage Negative Urine Samples in Phase 1 (ITT Population)
TABLE 14.2.6.2	Analysis of Percentage Negative Urine Samples in Phase 2 (ITT Protocol Population)
TABLE 14.2.7	Analysis Results for Percent of Subjects with Evidence of No Illicit Opioid Use by Time Point (ITT Population)
TABLE 14.2.8	Analysis Results for Cumulative Percentage of Subjects with Evidence of No

	Urine Illicit Opioid Use after 2 Month of Treatment by Time Point from Week 9 to Week 25 (ITT Population)
TABLE 14.2.9	Analysis Results for Percent of Subjects with No Self-Reported Illicit Drug Use by Time Point (ITT Population)
TABLE 14.2.10	Analysis Results for Percent of Subjects Meeting Criteria of Stability by Time Point (ITT Population)
TABLE 14.2.11.1	Analysis Results for Change from Baseline in Measures of Craving: Desire to Use VAS (ITT Population)
TABLE 14.2.11.2	Analysis Results for Change from Baseline in Measures of Craving: Need to Use VAS (ITT Population)
TABLE 14.2.12	Analysis Results for Change from Baseline in Measures of withdrawal: Clinical Opiate Withdrawal Scale (COWS) (ITT Population)
TABLE 14.2.13	Analysis Results for Change from Baseline in Measures of withdrawal: Subjective Opiate Withdrawal Scale (SOWS) (ITT Population)
TABLE 14.2.14	Analysis Results for Percent of Subjects without Evidence of Using Other Drugs of Abuse by Time Point (ITT Population)
TABLE 14.2.15	Analysis Results for Supplemental SL BPN (CAM2038 q1w 8 mg) Use (ITT Population)
TABLE 14.2.16	Analysis Results for Additional Supplemental Counseling (ITT Population)
TABLE 14.2.17.1	Analysis Results for Change from Baseline in Measures of Morning Need to Use (ITT Population)
TABLE 14.2.17.2	Analysis Results for Change from Baseline in Measures of Morning Desire to Use (ITT Population)
TABLE 14.3.1	Summary of Treatment Exposure (Safety Population)
TABLE 14.3.2	Summary of Treatment-Emergent Adverse Events (Safety Population)
TABLE 14.3.3	Summary of Columbia Suicide Severity Rating Scale (C-SSRS) (Safety Population)
TABLE 14.3.4.1	Summary of Percent of Subjects Who Reported Injection Site Related Pain, Itching, Discharge, Tenderness, Erythema/Redness, and Swelling by Time Point (Safety Population)
TABLE 14.3.4.2	Summary of Injection Site Related Pain Score by Time Point (Safety Population)
TABLE 14.3.4.3	Summary of Frequency of Injection Site Related Erythema/Redness and Swelling Severity by Time Point (Safety Population)
TABLE 14.3.5.1	Summary of All Treatment-emergent Adverse Events by System Organ Class and Preferred Term (Safety Population)
TABLE 14.3.5.2	Summary of All Injection Site Treatment-emergent Adverse Events by System Organ Class and Preferred Term (Safety Population)
TABLE 14.3.5.3	Summary of All Other (Non Injection Site Related) Treatment-emergent Adverse Events by System Organ Class and Preferred Term (Safety Population)
TABLE 14.3.6.1	Summary of All Treatment-emergent Adverse Events by System Organ Class, Preferred Term, and Intensity (Safety Population)
TABLE 14.3.6.2	Summary of All Injection Site Treatment-emergent Adverse Events by System Organ Class, Preferred Term, and Intensity (Safety Population)
TABLE 14.3.6.3	Summary of All Other (Non Injection Site Related) Treatment-emergent Adverse Events by System Organ Class, Preferred Term, and Intensity (Safety Population)

TABLE 14.3.7.1	Summary of All Treatment-emergent Adverse Events by System Organ Class, Preferred Term, and Relationship to Study Drug (Safety Population)
TABLE 14.3.7.2	Summary of All Injection Site Treatment-emergent Adverse Events by System Organ Class, Preferred Term, and Relationship to Study Drug (Safety Population)
TABLE 14.3.7.3	Summary of All Other (Non Injection Site Related) Treatment-emergent Adverse Events by System Organ Class, Preferred Term, and Relationship to Study Drug (Safety Population)
TABLE 14.3.8.1	Summary of All Suspected to Be Drug Related Treatment-emergent Adverse Events by System Organ Class and Preferred Term (Safety Population)
TABLE 14.3.8.2	Summary of All Suspected to Be Drug Related Injection Site Treatment-emergent Adverse Events by System Organ Class and Preferred Term (Safety Population)
TABLE 14.3.8.3	Summary of All Other (Non Injection Site Related) Suspected to Be Drug Related Treatment-emergent Adverse Events by System Organ Class and Preferred Term (Safety Population)
TABLE 14.3.9.1	Summary of All Serious Treatment-emergent Adverse Events by System Organ Class and Preferred Term (Safety Population)
TABLE 14.3.9.2	Summary of All Serious Injection Site Treatment-emergent Adverse Events by System Organ Class and Preferred Term (Safety Population)
TABLE 14.3.9.3	Summary of All Other (Non Injection Site Related) Serious Treatment-emergent Adverse Events by System Organ Class and Preferred Term (Safety Population)
TABLE 14.3.10.1	Summary of All Treatment-emergent Adverse Events That Lead to Study Discontinuation by System Organ Class and Preferred Term (Safety Population)
TABLE 14.3.10.2	Summary of All Injection Site Treatment-emergent Adverse Events That Lead to Study Discontinuation by System Organ Class and Preferred Term (Safety Population)
TABLE 14.3.10.3	Summary of All Other (Non Injection Site Related) Treatment-emergent Adverse Events That Lead to Study Discontinuation by System Organ Class and Preferred Term (Safety Population)
TABLE 14.3.11.1	Summary of All Serious Treatment-emergent Adverse Events That Lead to Study Discontinuation by System Organ Class and Preferred Term (Safety Population)
TABLE 14.3.11.2	Summary of All Injection Site Serious Treatment-emergent Adverse Events That Lead to Study Discontinuation by System Organ Class and Preferred Term (Safety Population)
TABLE 14.3.11.3	Summary of All Other (Non Injection Site Related) Serious Treatment-emergent Adverse Events That Lead to Study Discontinuation by System Organ Class and Preferred Term (Safety Population)
TABLE 14.3.12	Summary of All Deaths and Hospitalizations (Safety Population)
TABLE 14.4.1.1	Summary of Clinical Hematology Data (Safety Population)
TABLE 14.4.1.2	Shift from Baseline in Laboratory Tests: Hematology (Safety Population)
TABLE 14.4.1.3	Shift from Baseline in Laboratory Tests: > 3x the Upper Limit of Normal (ULN) for ALT, AST, and Doubling of Baseline Total Bilirubin (Safety Population)
TABLE 14.4.2.1	Summary of Clinical Chemistry Data (Safety Population)
TABLE 14.4.2.2	Shift from Baseline in Laboratory Tests: Chemistry (Safety Population)
TABLE 14.4.3.1.	Summary of Clinical Coagulation Profile Data (Safety Population)

TABLE 14.4.3.2	Shift from Baseline in Laboratory Tests: Coagulation Profile (Safety Population)
TABLE 14.4.4	Number (%) of Patients with Abnormal Physical Examination Findings (Safety Population)
TABLE 14.4.5	Summary of Vital Signs at Each Visit (Safety Population)
TABLE 14.4.6.1	Summary of 12-Lead ECG Conclusions (Safety Population)
TABLE 14.4.6.2	Summary of 12-Lead ECG Individual Parameters (Safety Population)
TABLE 14.4.6.3	Summary of 12-Lead Categories (Safety Population)
TABLE 14.4.7	Pregnancy Test (In clinic urine pregnancy test) (Safety Population)
TABLE 14.4.8	Pregnancy Test (Serum pregnancy test) (Safety Population)

List of Listings

Number	Title
LISTING 16.2.1.1	Patient Meets Inclusion Criteria (All Subjects)
LISTING 16.2.1.2	Patient Meets Exclusion Criteria (All Subjects)
LISTING 16.2.2	Eligibility for Randomization (All Subjects)
LISTING 16.2.3	Patient Randomization (All Subjects)
LISTING 16.2.4.1	Demographics (All Subjects)
LISTING 16.2.4.2	Medical History (All Subjects)
LISTING 16.2.4.3	Psychiatric History (All Subjects)
LISTING 16.2.4.4	Opioid and Substances Abused (All Subjects)
LISTING 16.2.5.1	Treatment (All Randomized Subjects)
LISTING 16.2.5.2	Injection Site Examination/ Treatment Compliance (All Subjects)
LISTING 16.2.5.3	Dosing Record (All Subjects)
LISTING16.2.6.1	Clinical Opiate Withdrawal Scale (COWS) (All Subjects)
LISTING16.2.6.2	Subjective Opiate Withdrawal Scale (SOWS) (All Subjects)
LISTING16.2.6.3	Opioid Craving VAS (All Subjects)
LISTING16.2.6.4	Illicit Drug Use Self Report (All Subjects)
LISTING16.2.6.5	Psychosocial Counseling (All Subjects)
LISTING16.2.7.1	Adverse Events (All Subjects)
LISTING16.2.7.2	Serious Adverse Events (All Subjects) (All Subjects)
LISTING16.2.7.3	Adverse Events That Lead to Study Drug Discontinuation (All Subjects)
LISTING16.2.7.4	Adverse Events That Have Death as the Outcome (All Subjects)
LISTING16.2.7.5	Death Report (All Subjects)
LISTING16.2.7.6	Prior and Concomitant Medications/Procedures (All Subjects)
LISTING16.2.8.1	Lab Test Samples (All Subjects)
LISTING16.2.8.2	Clinical Hematology (All Subjects)
LISTING16.2.8.3	Clinical Chemistry (All Subjects)
LISTING16.2.8.4	Clinical Coagulation Profile (All Subjects)
LISTING16.2.8.5	Urine Collection/Toxicology (General) (All Subjects)
LISTING16.2.8.6	Urine Toxicology (Illicit Opioids) (All Subjects)
LISTING16.2.8.7	Pregnancy Test (All Subjects)
LISTING16.2.8.8	Physical Examination (All Subjects)
LISTING16.2.8.9	Vital Signs (All Subjects)

LISTING16.2.8.10	12-Lead ECG (All Subjects)
LISTING16.2.8.11	C-SSRS (All Subjects)
LISTING16.2.8.12	Patient Disposition (All Subjects)
LISTING16.2.8.13	Protocol Deviations (All Subjects)

List of Figures

Number	Title
Figure 14.1.1	Responder Rate Per Primary Efficacy Definition (ITT Population)
Figure 14.1.2	CDF of Percent of Urine Samples Negative for Illicit Opioids Weeks 5-25 (ITT Population)
Figure 14.1.3	Time to sustained abstinence of opioid use (ITT Population)
Figure 14.1.4.1	Change from Baseline in Desire to Use VAS Over Time (ITT Population)
Figure 14.1.4.2	Change from Baseline in Need to Use VAS Over Time (ITT Population)
Figure 14.1.5.3	Change from Baseline in Morning Desire to Use VAS Over Time (ITT Population)
Figure 14.1.5.4	Change from Baseline in Morning Need to Use VAS Over Time (ITT Population)
Figure 14.1.6	Change from Baseline in Clinical Opiate Withdrawal Scale (COWS) Over Time (ITT Population)
Figure 14.1.7	Change from Baseline in Subjective Opiate Withdrawal Scale (SOWS) Over Time (ITT Population)
